The benefit of study participation is that the results of this study may be significant for future patients. nCLE is a promising safe, minimally-invasive imaging technique that, in conjunction with conventional endoscopic workup procedures, can provide real-time, high-resolution microscopic imaging of tissue characteristics within different organs in reach of bronchoscopy/endosonography. There is little burden related to study participation. After needle placement within the lymph node or lung tumor (standard procedure), we will hold the needle into place to obtain a CLE video.

Fluorescein, a commonly used stain in hospitals, will be administered (only in patients in the nCLE arm). In patients not at risk for allergic reactions to fluorescein (allergic reaction to fluorescein in the medical history), this is safe, and the risk of an adverse reaction is low (1.1 %). The most typical adverse reactions were mild, such as nausea (0.7%) [13]. Based on the fluorescein manufacturer's manual, patients with a known allergy to fluorescein and patients who used a beta-blocker within 24 hours before the intervention, and patients who are pregnant or lactating will be excluded. Based on the literature, we will not exclude patients with a previous reaction to another type of drug than fluorescein, as the literature shows that the incidence rate of an adverse reaction due to intravenous administration of fluorescein in 'special patient groups (such as: above 80 years old, drug allergy history, system disease) was similar to that in the healthy population. The estimated time for a bronchoscopic procedure is 25-35 minutes. The estimated prolonged endoscopy time for nCLE imaging is 10 minutes.

The patient will not notice anything due to the use of midazolam (fentanyl) or Propofol sedation (following standard procedure). Adverse events are not expected. A recent study by Karstensen et al. [28], combined EUS-FNA with nCLE in abdominal lymph nodes and pancreas, and no adverse events occurred during the 30-day follow-up. Also, no adverse events were reported in the study by Wijmans et al. [10] in the same target population. As stated by the hospitals, the standard diagnostic, therapeutic (lobectomy) process, and pathological evaluation, this study will not affect the internal protocol. In conclusion, we believe that the burden and risk associated with participation are negligible.

10. Administrative

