Transthoracic needle aspiration (TTNA) is currently the preferred mode for sampling peripheral pulmonary nodule (PPN) because it has a high diagnostic yield ranging from 80% to 90% [2]. However, it has a 12% to 45% risk of pneumothorax, with 2% to 15% requiring chest tube placement [3]. Flexible bronchoscopy with brushing, washing, and transbronchial biopsy (TBB) is safe but provides a much lower diagnostic yield (14 to 63%) depending on the size and location of PPN [4,5]. A recent meta-analysis including 1033 PPNs revealed that the diagnostic yield of TBB can reach up to 65%, if guidance systems such as electromagnetic navigational bronchoscopy (ENB), virtual bronchoscopy (VB), or radial-probe ultrasound (r-EBUS) are used. However, the negative predictive value (NPV) was reported to be low (0.52) [6,7].

Robotic technology has recently been incorporated into navigational bronchoscopy to improve flexibility, reach, and stability [8,9]. While manual and robot-assisted navigational bronchoscopy technologies have been proven effective in directing the bronchoscopist to achieve proximity to peripheral nodules, further localization with radial ultrasound and/or fluoroscopy is often required to make fine adjustments to align the biopsy needle with the target nodule. Without independent confirmation that a needle is in the lesion, a bronchoscopic lung biopsy that does not show tumor cells is often considered non-diagnostic rather than negative. Needle biopsies may therefore require multiple needle passes, which can cause bleeding. While rarely life-threatening, bleeding can contaminate slides and make a rapid on-site evaluation (ROSE) of biopsy samples challenging. A technology offering independent confirmation that the tip of the needle is within the nodule may reduce the incidence of non-diagnostic biopsies.

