The biopsy results can be classified into three categories: positive results, including malignant or benign lesions confirmed by a follow-up period, or negative results, including [18] intermediate histological samples, such as chronic inflammation, organizing pneumonia, or atypical cells without sufficient features to ascertain malignancy; or [22] indeterminate samples, such as normal lung tissue or insufficient sample size [6]. The tissue samples that produce intermediate and indeterminate samples should be further evaluated according to recommended guidelines for the management of pulmonary nodules.

In this study, the diagnostic yield of the bronchoscopic procedure (Robotic-guided TBNA or Robotic-nCLE-guided TBNA) will be defined as the proportion of patients in whom the bronchoscopic procedure yield a definitive diagnosis out of the total number of patients that have received the diagnostic procedure. This value is affected by the lesions' sizes, locations, and the existence of a bronchus sign or an airway leading directly into the lesion [23].

Primary objective:

To compare the first-pass diagnostic yield of the sequential needle passes (ROSE) between the Robotic-nCLE-guided TBNA arm and the Robotic-guided arm in PPNs.

Secondary objectives:

[figure not shown]
1. To compare the per-patient diagnostic yield (cumulative pass diagnostic yield: cumulative number of passes until five cumulated passes) of Robotic-nCLE-guided TBNA to that of Robotic-guided TBNA in PPNs.
2. To compare the proportion of patients with lung cancer treatment in the Robotic-nCLE-guided TBNA arm to that of the Robotic-guided TBNA arm in PPNs.
3. To compare the proportion of patients with follow-up (video-assisted thoracoscopic surgery (VATS) or TTNA or TBNA procedures in the Robotic-nCLE-guided TBNA arm to that of the Robotic-guided TBNA arm in PPNs.
4. To compare the number of passes needed to obtain a final diagnosis of Robotic-nCLE-guided TBNA to that of Robotic-guided TBNA in PPNs.
5. To assess the diagnostic performance (sensitivity, specificity, PPV, NPV, accuracy) of the sequential cumulative nCLE passes and the sequential cumulative ROSE passes using the final diagnosis as a reference.
6. To assess the feasibility by obtaining adequate CLE video footage in >80% of the PPN punctures.
7. To assess the safety of nCLE imaging, as defined by:

- a. The number and frequency of all AE/SAE from the start of the procedure until end of 12-month follow-up

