- b. The number and frequency of nCLE procedure-related AE/SAE from the start of the procedure until end of 12-month follow-up
- 8. To assess the reproducibility of nCLE criteria to the reference standard. Three nCLE characteristics for the detection of malignancy were identified during Wijmans et al. study [10]:
 - a. Dark enlarged pleomorphic cells;
 - b. Dark cell clusters consist of overlapping cell structures ('dark clumps') and
 - c. Continuous movement of the cells in one direction ('directional streaming').
- 9. To create an nCLE image atlas for malignant characteristics in PPNs.

3. Study Design

This is a randomized, controlled, interventional, comparative prospective multi-center study. In total, a maximum of 118 consecutive patients with a (suspected) PPN who are referred for a diagnostic bronchoscopic (Robotic-guided TBNA) procedure will be considered for enrollment. The estimated duration of the study is 24 months. Patients will be consecutively recruited and randomly assigned to undergo Robotic-guided TBNA (n=59) or Robotic-nCLE-guided TBNA (n=59).

Only patients in the nCLE arm will receive intravenously administered fluorescein before the start of the Robotic procedure. During the nCLE procedure, an 18G needle enters the targeted tissue, followed by an nCLE AQ-Flex™ 19N Confocal Miniprobe™ (Mauna Kea Technologies, France) through the biopsy needle, to obtain real-time imaging. nCLE imaging will be performed in the PPNs with a total estimated time for research measurements of 10 minutes. nCLE imaging will be performed for each sequential TBNA pass/sampling within the lung nodule lesion and each TBNA path cytopathological result will be correlated with the nCLE sequence acquired for that TBNA pass. TBNA sampling will end when sufficient diagnostic material will be found with ROSE (as assessed by the cytopathologist) or when the physician performing the procedure judges that the number of samplings/passes is adequate. ROSE will be performed by a cytopathologist.

4. Study Population

Population (base)

Patients with a PPN referred for diagnostic bronchoscopic/endosonographic workup tissue sampling based on standard (PET-) CT imaging

Inclusion criteria

To be eligible to participate in this study, a study subject must meet all of the following criteria:

- ≥ 21 years of age
- Suspected PPN
- Nodule size in CT between 8 mm and 30 mm (largest dimension)

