- Ability to understand and willingness to sign a written informed consent and HIPAA consent document

Exclusion criteria

- Inability or non-willingness to provide informed consent
- Failure to comply with the study protocol
- Patients with known allergy for fluorescein or risk factors for an allergic reaction
- Use of beta-blocker within 24 hours before the start of the bronchoscopic procedure
- Possibly pregnant, pregnant or breastfeeding women
- Patients with hemodynamic instability
- Patients with refractory hypoxemia
- Patients with a therapeutic anticoagulant that cannot be held for an appropriate interval before the procedure
- Patients who are unable to tolerate general anesthesia according to the anesthesiologist
- Patient undergoing chemotherapy

Intra-operative Exclusion/Stopping Criteria:

- The lesions are unable to be localized/confirmed by bronchoscopy
- The procedure will be terminated if the patient develops a significant procedural complication as determined by the treating physician
- The procedure will be terminated if the patient develops hemodynamic instability as determined by the treating physician

Sample size calculation

A bronchoscopic TBNA (Robotic-guided TBNA or Robotic-nCLE-guided TBNA) will be regarded as successful when histological confirmation of the diagnosis is achieved and matches the final diagnosis. If additional TBNA passes or tests, e.g., further bronchoscopies, surgery, etc., are needed to establish the diagnosis, the TBNA pass will be regarded as non-diagnostic.

We will calculate TBNA diagnostic yield for the cumulative number of passes until five cumulated passes for both the Robotic-guided TBNA and Robotic-nCLE-guided TBNA arms. It is anticipated that sequential passes at a target site will result in stepwise yield increments to a plateau. Every needle pass at a location will be reported separately and entered into a database to provide yields after each sequential pass.

Proportional data will be compared using a Chi-squared test of contingency tables or Fisher's exact test on 2x2 contingency tables in the case of very small counts (<5).

First- and cumulative-pass diagnostic yields:

Diagnostic yields for the different cumulative passes are defined as follows:

1. First-pass diagnostic yield is calculated as the proportion of patients for which first-pass TBNA during the bronchoscopic procedure yielded a definitive diagnosis out of the total number of patients that have received a diagnostic procedure.

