2. First-two-passes cumulative diagnostic yield is calculated as the proportion of patients for which first-two-passes cumulative TBNA pass during the bronchoscopic procedure yielded a definitive diagnosis out of the total number of patients that have received a diagnostic procedure.
3. First-three-passes cumulative diagnostic yield is calculated as the proportion of patients for which first-three-passes cumulative TBNA pass during the bronchoscopic procedure yielded a definitive diagnosis out of the total number of patients that have received a diagnostic procedure.
4. Etc.... until the fifth pass.

The number of patients has been calculated to demonstrate an increase of the TBNA first-pass diagnostic yield by 20%, from 70% to 90%, between the Robotic-guided TBNA and the Robotic-nCLE-guided TBNA, with a statistical power of 80% with a 2-sided significance level of 0.05. A group size of 59 patients per arm has been derived. By including 59 patients in each arm, we expect to image at least 29 malignant nodules (prevalence of 0.5) in each arm.

The study will enroll 118 consecutive patients randomly assigned 1:1 to Robotic-guided TBNA arm or Robotic-nCLE-guided TBNA arm.

5. Treatment of Subjects

Investigational product/treatment

In recent years, confocal laser endomicroscopy (CLE) has emerged as a novel technique that enables *in vivo* microscopic analysis during ongoing endoscopy [24]. CLE is based on tissue illumination with a low-power laser with subsequent detection of the fluorescence light reflected from the tissue. It is a contrast-based technique, the most widely used agent being the intravenously administered fluorescein. The probe of the endomicroscopy system consists of a flexible catheter probe representing a bundle of optical fibers linked to a micro-objective, a laser scanning unit, and the control and acquisition software (Cellvizio® I.V.E system, Mauna Kea Technologies, France). The principle of the technique is based on a laser beam of the defined wavelength being focused towards the targeted tissue, and the recaptured signal is displayed as 'optical biopsies' in a single horizontal plane.

[figure not shown]

Figure 1: A- Locking of the CLE probe to the aspiration needle. B- CLE probe inside endosonography needle. C- Endosonography images of n-CLE measurements (white arrow) inside a lymph node (LN) (Wijmans/Annema et al. [10]).

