All patients will be evaluated for adverse events (AEs) and serious adverse events (SAEs) at the procedure day, 7 days, and 30 days post-procedure. On the day of the procedure the principal investigator will evaluate possible signs and symptoms such as shortness of breath, chest pain, dizziness, low blood oxygen saturation ($\geq 90\%$), hemoptysis (cough bright red blood) and fever ($> 37.3\text{ C}$). At Day 7(post procedure), a study team will contact the patient by the phone and ask about any symptoms of shortness of breath, chest pain, cough with yellow or greenish sputum, hemoptysis (cough bright red blood) and fever. At Day 30, the study team will review patient's medical records and collect data of medications, doctor visits (primary care and specialist visits), procedures and other medical records information. In addition, patients will be instructed to call in with concerns and/or present to the research staff or Principal Investigator. . The study staff will be recording and reporting in the electronic medical record all the adverse events with an attribution of possibly, probably, or definitely related to the study intervention.

Depending on the event, follow up may require additional tests or medical procedures as indicated and/or referral to the general physician or a medical specialist.

Stopping rules based on safety considerations

Investigators will be responsible for data and safety monitoring for this trial. Investigators will discuss with the statistician and/or the study Sponsor if higher than expected rate of adverse events of unacceptable grades are documented. If the rate is more than 10 % of the patient with bleeding, more than 5% with pneumothorax or respiratory failure and 1 patient with anaphylaxis, the principal investigator will consider stopping the study. Statistician and/or Sponsor, after discussion with the Investigator, may recommend to close the study to IRB if the rate of study related adverse events is between the parameters mentioned previously.

6. Data Collection

Subject demographics

- Age
- Sex
- Ethnicity
- Race

Subject medical history and baseline status

- Prior invasive lung procedures and surgeries
- Lung function and diffusing capacity
- Antithrombotic medication current and prior status, including duration of any discontinuation
- Subject risk factors
- Pre-procedure probability of malignancy

Lesion characteristics

- Size
- Location
- Presence of bronchus sign on computerized tomography (CT)

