The tumor board will determine intermediate diagnosis and management recommendations for each patient at the intermediate and final diagnosis phases (see Figure 3). Three therapeutic management options will be considered: "neither treatment nor follow-up", "follow-up", or "treatment" (see above). If the diagnosis is certain, "neither surgery nor surveillance" will be recommended for benign nodules; treatment will be recommended for malignant lesions; either treatment or follow-up will be recommended for indeterminate nodules.

An intermediate diagnosis and an intermediate management recommendation will be provided after the tumor board receives TBNA histological results and recorded in the Case Report Form for each patient of both arms.

A final diagnosis and a final management recommendation will be provided just after the final diagnosis results are received by the tumor board and recorded in the Case Report Form for each patient of both arms.

These intermediate diagnosis and management recommendations will also be compared to the definitive diagnosis and final patient management decisions.

7. Statistical Analysis

Population demographics comparison in both arms:

Statistical analysis will be performed to compare the patient population in terms of demographics to assess whether there are any differences between the populations of the two arms in terms of age, sex, race, type of lung cancers, and cancer prevalence.

Lesion characteristics comparison in both arms:

Statistical analysis will be performed to compare the lesion characteristics to assess whether there is any difference in lesion characteristics between the two arms, in terms of size, location of the nodule, Presence of bronchus sign on computerized tomography, lung zone, positive PET, associated lymphadenopathy, distance closest to fissure, distance from lesion to pleura, and pre-procedure probability of malignancy.

Navigation Accuracy

Distance between the tip of the locatable guide/nCLE Confocal MiniprobeTM and the targeted lung lesion will be measured for each nodule. The median and standard deviation of the distance will be calculated for both arms. Using a statistical test (Student T-test), they will be compared between arms (Robotic-guided TBNA and Robotic-nCLE-guided TBNA).

Navigation success

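### Cheap improvement, not an error: lesion size and bronchus sign are recorded and said to affect yield, but first-pass yield is compared unadjusted; adjusting changes power by about -0.6 to +5 points

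*Combined protocol and SAP*

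**What the plan says.** The background section, just before the objectives, defines the diagnostic yield of the bronchoscopic procedure and adds: "This value is affected by the lesions' sizes, locations, and the existence of a bronchus sign". The statement concerns the whole procedure and gives no effect sizes.

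Section 6 (Lesion characteristics) lists size, location and CT bronchus sign among the data to collect. CT size is also an entry criterion in section 4, with limits of 8 and 30 mm.

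For the analysis, section 4 (Sample size calculation) states: "Proportional data will be compared using a Chi-squared test of contingency tables", with Fisher's exact test for counts below 5. Section 7 (First- and cumulative-pass diagnostic yields) adds 95% confidence intervals and a p-value and mentions no covariates. The only planned use of the lesion factors is in section 7 (Lesion characteristics comparison): "Statistical analysis will be performed to compare the lesion characteristics to assess whether there is any difference in lesion characteristics between the two arms". Nothing says what follows if a difference is found.

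On size: "A group size of 59 patients per arm has been derived", for 70% v 90% first-pass yield, 80% power and two-sided 0.05. Allocation is 1:1. The text available names no stratification factor, but part of the background section and Figure 3 could not be read.

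**The concern.** The plan names factors that it believes drive yield, collects them before the procedure, and then uses them neither in allocation (as far as the text shows) nor in the primary comparison. If they affect first-pass success, adjusting for them would estimate the same risk difference somewhat more tightly, with no new data. This matters a little more than usual because power sits exactly at target.

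The balance comparison could also show a chance difference in bronchus sign between arms. With no planned response, any adjustment made then would be chosen after the fact and open to challenge.

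**Working it through.** **Inputs from the documents (section 4).** Yields 0.70 and 0.90; two-sided alpha 0.05; power 80%; 59 per arm; chi-square, or Fisher for counts below 5 (read here as observed counts).

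**1. The plan's sample size.** Unpooled formula: n = (1.960 + 0.842)² × [0.7(0.3) + 0.9(0.1)] / 0.20² = 7.849 × 0.30 / 0.04 = 58.87, so 59. This matches.

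**2. Operating characteristics of the planned test.** Exact enumeration at 59 per arm gives power of 79.96%. Exact type I error is 5.2% with both arms at 70%, 5.2% at 80% and 2.3% at 90%, where Fisher mostly applies. The SE of the difference is √(0.30/59) = 7.1 points.

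**3. Room for covariates.** Expected first-pass failures are 59 × 0.30 + 59 × 0.10 = 17.7 + 5.9, about 24. That supports two covariates, not many.

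**4. Power with adjustment.** These inputs are assumptions, because the documents give no effect sizes. Trials were simulated with 59 per arm, marginal yields fixed at 70% v 90%, bronchus sign in 50%, and 40,000 runs per scenario (Monte Carlo SE of a power about 0.2 points). Each cell is plan v adjusted power in %, with the change in points.

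| Odds ratios (bronchus sign; size per SD) | Same effect in both arms | Log odds ratio halved in nCLE arm | Control arm only |
|---|---|---|---|
| 1; 1 | 80.0 v 79.6 (-0.4) | – | – |
| 1.5; 1.25 | 79.6 v 79.6 (0.0) | 79.8 v 79.6 (-0.2) | 80.0 v 79.6 (-0.4) |
| 2; 1.5 | 80.1 v 81.3 (+1.2) | 80.0 v 80.6 (+0.6) | 79.7 v 79.8 (+0.1) |
| 3; 1.5 | 79.8 v 81.9 (+2.1) | 80.0 v 81.1 (+1.1) | 80.0 v 80.4 (+0.4) |
| 3; 2 | 79.6 v 83.1 (+3.5) | 80.2 v 82.3 (+2.1) | 79.8 v 80.6 (+0.8) |
| 4; 2 | 80.1 v 84.7 (+4.6) | 79.9 v 82.3 (+2.4) | 80.0 v 81.0 (+1.0) |

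With bronchus sign in 30% or 70%, the range is -0.6 to +4.9. With 10% of bronchus sign missing and filled in, and no prognostic effect, the change is -0.6.

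**5. The same gain in patients.** Use 118 × (1/variance ratio - 1), with ratios at odds ratios (2; 1.5) and (4; 2).
- Both arms alike: 0.979 and 0.891, so about 2.5 and 14 patients.
- Halved in the nCLE arm: 0.993 and 0.933, so about 1 and 8.
- Control only: 1.004 and 0.968, so about -0.5 and 4.

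**6. Chance imbalance.** A bronchus-sign difference of 15 points or more between arms occurs in about 8-12% of trials. At odds ratios of 2-4 it shifts the unadjusted difference by 1.7-3.6 points if effects are common, and by about 1-2.6 points if they act in the control arm only. The adjusted difference still shifts, by up to about 0.5 points.

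**7. Type I error of the adjusted test.** It is 5.0-5.5% at 70-80% yield, with CI coverage of 94.3-95.1%. It rises when failures are scarce:

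| Both arms at | Plan | Adjusted, no guard | Adjusted, with guard |
|---|---|---|---|
| 90% | 2-3% | 5-6% | about 3% |
| 95% | about 1% | 7-8% | about 1% |

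The guard hands the p-value back to the plan's rule when total failures are under 12. From the binomial distribution, P(failures ≤ 11 of 118) is 0.48 at 90% and 0.98 at 95% in both arms. At 70% v 90% it is 0.001, so power there is essentially unchanged.

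**The case against.** The strongest reply is that nothing is broken. A pre-specified unadjusted comparison that matches the sample-size basis is legitimate in a randomised trial. That stands, and it is why this is an improvement only. A reader might infer that the primary result would be biased or the trial underpowered; the documents support neither.

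The premise is also partly inferred: the background statement concerns the whole procedure, and its extension to the first pass is a step the plan does not take. The plan's own rationale points to weaker effects in the nCLE arm: "A technology offering independent confirmation that the tip of the needle is within the nodule may reduce the incidence of non-diagnostic biopsies". The size limits, and the intra-operative exclusion where "The lesions are unable to be localized/confirmed by bronchoscopy", may weaken them further. So the upper end of the gain, which needs odds ratios of 4 and 2 acting equally in both arms, is the least supported. This stands.

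Two tempting overstatements also fall. Adjustment is not a sure gain, since small losses are possible. Nor does it wholly remove the imbalance shift, which is in any case well inside the 7.1-point SE and allowed for by the planned interval.

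Finally, the unguarded adjusted test can exceed 5% when both yields are very high. That objection is sound, and the guard answers it. What survives is that the factors are the plan's own, are already collected, and have no pre-specified role in the primary analysis.

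**Conclusion.** A cheap improvement worth considering, with medium confidence. The planned analysis is valid, unbiased and powered at 80.0%. Adjusting for CT size and bronchus sign changes power by about -0.6 to +5 points under the assumed odds ratios (1-4 and 1-2 per SD). The loss is under 1 point if the factors are not prognostic, and the change is about 0 to +1 if they act in the control arm alone. Adjustment also reduces a 1-3.6 point shift, seen only in the 8-12% of trials with a marked bronchus-sign imbalance, to within about 0.5 points. The size and even the sign of the power change depend on effect sizes that the documents do not give. The absence of stratification is judged only on the text that could be read.

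**What to change.** Before outcomes are seen, write into section 7:

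- **Primary estimate:** the covariate-standardised risk difference from a logistic model of first-pass success on arm, CT lesion size (mm, continuous) and bronchus sign (yes/no). Location is left out because it needs several categories and only about 24 failures are expected.
- **Inference:** p-value and 95% CI from that one estimate, with the influence-function variance multiplied by N/(N-4) and a t reference with N-4 df.
- **Missing bronchus sign:** fill with the most frequent value, ignoring arm.
- **Fallback:** a Firth-penalised fit if the model does not converge or an arm has all or no successes.
- **Guard:** if first-pass failures across both arms are few (for example under 12), take the p-value from the plan's chi-square/Fisher rule.
- **Sensitivity analysis:** the unadjusted chi-square/Fisher result. Present lesion characteristics by arm descriptively.

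If the sponsor judges the gain too small to change the primary test, pre-specify the adjusted estimate as supportive.

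Cost: SAP wording and modest programming, with no new data. Downsides are under 1 point of power if the covariates are not prognostic, and a less conservative test near 90% yield in both arms (about 3% with the guard, against 2-3%). When the guard applies, the p-value and the adjusted CI come from different methods and could disagree. The Firth fit is needed in 0.2-4% of trials at 70% v 90%. With both arms at 90% it is needed in about 1-7% when half have a bronchus sign, and in 27% in the worst case tried.
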